## 7.3 Statistical Methods

### Descriptive Statistics

Baseline characteristics will be descriptively summarized using mean and standard deviation for continuous variables that have a normal Gaussian distributions, and median and interquartile range for continuous variables with a skewed distribution. Frequencies and percentages will be used to summarize categorical baseline characteristics. Baseline characteristics will be compared between the intervention and control groups using the two-sample t-test, Wilcoxon rank sum test, and chi square test, as appropriate.

### Handling of Missing Data

Subjects with missing data for the primary outcome will be excluded. Otherwise, missing data will be tracked and reported separately. If the amount of missing data within an analysis is greater than 10%, imputation methods will be used and the data re-analyzed as a sensitivity analysis.

### Multiplicity

We will only evaluate outcomes determined a priori and will report all analyses.

### Primary Hypothesis:

We hypothesize that the mean pre-delivery length of stay will be significantly less in the intervention group as compared to the control group. The mean time spent in the hospital between the groups will be compared using a 2-sample t-test or the nonparametric equivalent (Wilcoxon Rank-Sum test).

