## Study Summary

Title	Outpatient Foley catheter compared to usual inpatient care for cervical ripening: A non-randomized prospective study
Running Title	Outpatient vs. inpatient cervical ripening
Protocol Number	14-008988
Phase	Pivotal
Methodology	Prospective
Overall Study Duration	24 months
Subject Participation Duration	4-36 hours
Single or Multi-Site	Single site
Objectives	To compare the length of pre-delivery hospitalization in pregnant women undergoing cervical ripening with a Foley catheter in the outpatient setting compared with standard methods administered in the inpatient setting.
Number of Subjects	40 Outpatient Foley Subjects + 160 standard of care subjects Total of 400 women and their babies
Diagnosis and Main Inclusion Criteria	Pregnant women at $\geq$ 37 weeks gestation who are scheduled for induction of labor and who have an unfavorable cervical exam (Bishop score <9 and cervical dilation <3cm)
Study Product, Dose, Route, Regimen	The Foley catheter is a single balloon catheter that is placed transcervically by a provider and inflated with 60cc of normal saline. It mechanically dilates the cervix to 3-4cm over several hours.
Duration of Administration	The device will remain in place until it passes through the cervix, generally when the cervix is dilated to 3-4 cm, which typically occurs 3-12 hours after placement.
Reference therapy	Cervical ripening in the inpatient setting with either a Foley catheter and/or vaginal misoprostol 25 mcg tablets every 4 hours.
Statistical Methodology	The mean time of pre-delivery hospitalization between outpatient Foley catheter and inpatient usual care groups will be compared using a two sample t-test or the nonparametric equivalent Wilcoxon rank sum test. Secondary endpoints will be compared using two sample t-tests or the nonparametric equivalent Wilcoxon rank sum test for continuous endpoints or the chi-Square or Fisher's exact test for categorical endpoints.

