## 3 Study Design

### 3.1 General Design

The study began as a randomized control trial. The intervention group was comprised of low risk pregnant women who had a Foley catheter placed followed by dismissal home with return in approximately 12 hours for continuation of the labor induction process. The control group consisted of women who remained inpatient during the entire cervical ripening phase followed by continuation of the labor induction process in the inpatient setting.

Due to difficulty enrolling women for the randomized control trial, a prospective design with an outpatient intervention group (Foley catheter) and matched inpatient control comparison group is proposed. Low risk pregnant women will be invited to participate in an outpatient Foley catheter intervention to begin their induction of labor process. Maternal/Neonatal outcomes and maternal satisfaction with the induction experience will be assessed. The comparison group will be enrolled to participate in the study in a limited way, providing responses to a maternal satisfaction of induction survey and allowing their and their baby's electronic medical record to be followed for maternal/neonatal health outcomes and total hospital time.

- I. Enrollment of participants (Randomized Control Trial)
  - A. Clinic nurses, clinical assistants who room patients, and the patient's obstetric provider will refer eligible patients to the research coordinator.
  - B. The Co-PI ([name]) will monitor the induction scheduling book in the Family Birth Center two weeks in advance to identify patients who may be eligible for the study. She will communicate the patient's next clinic appointment to the research coordinators so these patients can be approached in clinic.
  - C. Patients who receive their care in Mayo Clinic Family Medicine clinics will be eligible for this study. Their providers will be educated regarding this trial.
- II. Patient education, consent, and randomization
  - A. The patients will be educated about induction of labor, the Foley catheter, and the proposed research study.
    1. The patient will be approached for this education during their last or second to last clinic visit before planned induction of labor.
    2. The education will be performed by a trained research coordinator, Principal Investigator, Co-Principal Investigator, or authorized obstetric provider.
  - B. If the patient elects participation, she will undergo informed consent at that time.

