#### B. Enrollment of inpatient comparison (usual care) participants

1. Women who decline participation in the outpatient intervention study may be approached to participate in a limited way as inpatient comparison control participants.
2. The study coordinator will screen the OB White Board daily in the Family Birth Center to identify patients presenting for induction of labor who may be eligible for the study, but not captured during the weekly screening process. Eligible women will be approached, after discussion with their attending obstetric provider, to participate in the study as inpatient comparison usual care participants.
3. Four inpatient comparison control participants will be enrolled with the same parity and BMI strata for every outpatient intervention patient enrolled (see III. A. 3. c. above).

- (a) Patient education and consent
  - (a) The patients will be educated the proposed research study.
  - (b) If the patient elects participation, she will undergo informed consent at that time by a trained research study

coordinator, Principal Investigator, Co-Principal Investigator, or authorized obstetric provider.

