A. If the patient is in the outpatient control group, she will arrive to the Family Birth Center at a standard, predetermined time (typically 0730 or 1930) to undergo induction of labor.

B. Method of cervical ripening

1. The only pharmacologic cervical ripening agent to be used is vaginal misoprostol, 25 mcg every 4 hours with a maximum of six doses.
2. She may or may not have a Foley catheter placed as a method of cervical ripening based upon the providing team's discretion.
3. A Foley catheter will be favored during the cervical ripening phase if there is tachysystole and/or a nonreassuring fetal heart tracing precluding further misoprostol administration, provided the Bishop score is still  $<6$ .

C. After cervical ripening is achieved, oxytocin and/or artificial rupture of membranes will be used at the discretion of the providing team.

D. If oxytocin is used during the labor induction, the dose will be increased as determined by the Family Birth Center Oxytocin low dose infusion regimen.

E. The remainder of her care during the first, second, and third stages of labor will be at the discretion of the providing team.

F. All patients' labor progress will be monitored using a partogram. Cesarean delivery will not be performed for arrest of labor or failed induction unless all criteria have been met as outlined by the Family Birth Center Workgroup protocol made effective 6/2/14.

VI. Protocol for the inpatient usual care group (Prospective Study)

A. All methods of cervical ripening and labor augmentation will be at the discretion of the providing team. Cervical ripening will occur as described above with vaginal misoprostol and a Foley catheter; dinoprostone (vaginal prostaglandin, brand name Cervidil) is infrequently used in the Family Birth Center but would now be an option as well. Oxytocin dosing will be increased by the FBC oxytocin low dose infusion regimen, labor will be monitored using a partogram, and Cesarean delivery will continue to be determined by the criteria as described above.

VII. Follow-up

[figure not shown]
A. Inpatient follow-up

1. We will obtain maternal consent to abstract secondary endpoints as described in section 3.3 from the fetal and maternal electronic medical record.

[figure not shown]
B. Follow-up over 6 weeks

1. Secondary endpoints from section 3.3 will be abstracted from the EMR.  

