### 3.3 Secondary Study Endpoints

#### I. Baseline maternal data

##### A. Date of birth

- B. Race and ethnicity
- C. Pre pregnancy body mass index
- D. Gravidity
- E. Parity
- F. Medical comorbidities
- G. Surgical history
- H. Major complications during this pregnancy (i.e. gestational diabetes)
- II. Intervention (outpatient) group data
  - A. Method of Foley catheter insertion: digital or sterile speculum
  - B. Foley catheter expulsion at home: yes/no, time of expulsion
  - C. Return to the Family Birth Center earlier than scheduled and reason (labor, rupture of membranes, decreased fetal movement, vaginal bleeding, pain, fever, or other)
  - D. Bishop score before Foley placement
  - E. Bishop score on the morning of admission for continuation of the labor induction
  - F. First induction method used after admission in the morning
    - a. Oxytocin
    - b. Artificial rupture of membranes
    - c. Oxytocin + artificial rupture of membranes
    - d. If Foley catheter still in place, Foley + oxytocin
- III. Procedural data for both groups
  - A. Gestational age at delivery
  - B. Primary providing team in the Family Birth Center (Obstetrics, Midwifery, or Family Medicine)
  - C. Use of Foley catheter: yes/no, date and time
  - D. Use of pharmacologic cervical ripening: yes/no, date and time, number of doses
  - E. Use of oxytocin: yes/no, date and time, maximum dosage
  - F. Rupture of membranes: spontaneous or artificial, date and time
  - G. Epidural placement: yes/no, date and time
  - H. IV pain medication administration prior to delivery—time, medication, and dose
  - I. Date and time of delivery
  - J. Number who delivered within 12, 24, 36, 48 hours from initiation of cervical ripening
  - K. Number who delivered before midnight of the following day
  - L. Meconium passage prior to delivery: yes/no, thin or thick
  - M. Total number of cervical exams
  - N. Mode of delivery
    - 1. Normal spontaneous vaginal delivery
    - 2. Vacuum assisted vaginal delivery and indication
    - 3. Forceps assisted vaginal delivery and indication
    - 4. Cesarean delivery
  - O. If a cesarean delivery was performed:
    - 1. Indication for cesarean (non-reassuring fetal heart status, umbilical cord prolapse, uterine rupture, placental abruption, failed operative delivery, arrest of dilation, arrest of descent, and other)
    - 2. Type of cesarean—emergent, urgent, or non-urgent (“Alpha,” “Beta,” or “Charlie”)

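### The non-randomised primary comparison has no covariate adjustment, so any imbalance in unmatched factors that predict pre-delivery hours stays in the estimated effect

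*Combined protocol and SAP*

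**What the plan says.** Section 3.1 explains the change of design: "Due to difficulty enrolling women for the randomized control trial, a prospective design with an outpatient intervention group" and a matched inpatient group replaces the randomised trial.

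Controls come from two sources (section 3.1, III.B):
- Item 1: "Women who decline participation in the outpatient intervention study may be approached to participate in a limited way as inpatient comparison control participants".
- Item 2: women seen on the daily white-board screen, described as "patients presenting for induction of labor who may be eligible for the study, but not captured during the weekly screening process".

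The mix of the two is not stated. Matching is covered in item 3: "Four inpatient comparison control participants will be enrolled with the same parity and BMI strata for every outpatient intervention patient enrolled".

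The Study Summary gives the primary analysis as follows: "The mean time of pre-delivery hospitalization between outpatient Foley catheter and inpatient usual care groups will be compared using a two sample t-test", with the Wilcoxon test as the alternative. Section 7.3, Primary Hypothesis, repeats it: "The mean time spent in the hospital between the groups will be compared using a 2-sample t-test or the nonparametric equivalent (Wilcoxon Rank-Sum test"). Sections 7.3 and 7.4 contain no regression, stratified or matched analysis, propensity method or adjusted sensitivity analysis. Baseline characteristics are to be summarised and tested between groups, but nothing follows from the result.

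On data, section 3.1, VII.A says: "We will obtain maternal consent to abstract secondary endpoints as described in section 3.3 from the fetal and maternal electronic medical record". In section 3.3 the item "Bishop score before Foley placement" is II.D, under data for the outpatient group. It is not among the baseline maternal data (I) or the procedural data for both groups (III).

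**The concern.** Randomisation would have balanced prognostic factors on average, so an unadjusted test was defensible for the first design. The two matching factors were the stratifiers of that design. They were carried over, but nothing replaced randomisation for the other factors.

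The comparison is now between women who accept going home with a catheter and women who either declined or were missed by weekly screening. Cervical state at the start is an obvious prognostic factor. Section 1.1 reports that a favourable cervix is variably defined as a Bishop score of at least 6 or at least 8, and section 4.1 admits scores below 9. Eligible women therefore range from clearly unfavourable to favourable on the protocol's own definitions. If the groups differ on such a factor, the unadjusted difference mixes that imbalance with the effect of setting. The primary objective is a comparison of mean hours, so a shifted estimate matters even when the p-value is secure.

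**Working it through.** **Inputs.** From section 7.2: 40 and 160 women, SD 8 h, means 16 and 12 h (difference 4 h), two-sided alpha 0.05, power 80%. From section 7.1: published reductions of 9.6 h and 11.1 h. The documents give no bias size, covariate effect or imbalance. All such values below are assumptions.

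**1. The plan's own figure.** SE = 8 × √(1/40 + 1/160) = 1.414 h. With a noncentral t on 198 df, power for 4 h is 80.4%. The stated 80% reproduces; it presumes an unbiased comparison. The smallest significant difference is 1.972 × 1.414 = 2.79 h.

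**2. Effect of an assumed net bias b.** Rejection under no effect is the two-sided noncentral-t probability with noncentrality b/SE. Coverage of the 95% CI is one minus that, whatever the true effect.

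| Quantity | b = 0 | b = 1 h | b = 2 h |
|---|---|---|---|
| Coverage of 95% CI | 95% | 89.2% | 70.9% |
| Rejection, no true effect | 5% | 10.8% | 29.1% |
| Power for 4 h, bias opposing | 80.4% | 56.0% | 29.1% |
| Power for 9.6 h, bias opposing | >99.9% | >99.9% | >99.9% |
| b as share of 4 h | – | 25% | 50% |
| b as share of 9.6 h | – | 10% | 21% |
| b as share of 11.1 h | – | 9% | 18% |

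If only decliners differ from acceptors, and they are a fraction f of controls, the net bias is f × b. A 2 h difference with f = 0.5 gives 1 h.

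**3. What adjustment recovers.** A simulation used 6,000 runs, exact 4:1 matching and a linear model with group, parity, BMI class, Bishop score and gestational age, with HC3 standard errors. The 2 h bias was built from a Bishop imbalance of 0.5 SD (correlation with the outcome 0.4) and a gestational-age imbalance of 0.25 SD (correlation 0.2).
- Unadjusted: bias 2.0 h, coverage 71–72%.
- Adjusted, Bishop score free of error: bias 0.03 h, coverage 95%.
- Adjusted, Bishop reliability 0.7: bias about 0.5 h, coverage 93%.

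Here all of the bias comes from covariates in the model. If half of the 2 h is unmeasured, 1 h remains. The adjusted SE is 1.414 × √(VIF × (1 − R²)). With VIF 1.04–1.08 and R² 0–0.3, coverage is about 87–90%, and about 86% with Bishop reliability 0.7.

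**4. Cost in power.** For k uncorrelated covariates, each imbalanced by 0.5 SD, VIF = 1 + k × 0.5² × 0.2 × 0.8. With k = 2, VIF = 1.08 and the SE rises by √1.08 − 1 = 3.9%. If the covariates explain nothing, power for 4 h is 77.3% (75% simulated with HC3). Break-even R² = 1 − 1/1.08 = 7.4%. At R² = 10%, power is 81.5%.

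**The case against.** The strongest reply is that no imbalance has been shown and that the design already controls a good deal. Parity and BMI class are balanced by enrolment, so ignoring those strata adds no bias from them. Sections 4.1 and 4.2 also restrict many factors for everyone: singleton cephalic pregnancy, fluid index, dilation, prior cesarean, growth restriction and pregestational diabetes, with induction indication and timing tied to a unit guideline. This stands. A reader might infer that nothing beyond parity and BMI is controlled, or that every baseline difference biases the result. Neither follows: restriction removes or narrows several differences, and only imbalance in a factor that predicts pre-delivery hours causes bias. It does not dispose of the point, because restriction leaves a range within which Bishop score and gestational age can still differ.

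A reader might also infer that Bishop score is unavailable for controls. The documents do not support that. The score is needed for eligibility (section 4.1), and section 6.2 gives all patients a cervical exam on arrival. However, a Bishop calculation is written only into the intervention procedures (section 3.1, IV.D). The case report form is not in the documents, so the gap is shown for section 3.3 only.

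Nor are all controls decliners. Women missed by weekly screening are not shown to have refused anything, and they may dilute a preference effect.

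Finally, the return to 95% coverage is partly built into the simulation. With unmeasured preference in play, the gain is smaller, as step 3 shows. The choice of covariates, and of the adjusted model as primary rather than supporting, is a judgement that the documents do not settle.

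**Conclusion.** The point holds and should be fixed. The only primary analysis is unadjusted, the comparison is non-randomised, and matching covers two factors. Prognostic imbalance in the remaining factors would pass straight into the estimate, with unknown size and direction.

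It would go too far to say that the trial's conclusion is likely to be false. If the true reduction is near the 9.6 or 11.1 h that the protocol cites, a bias of 1 to 2 h leaves detection secure. The harm is then a mis-sized estimate whose confidence interval misses too often. Only near the 4 h design value, or with no effect, does a missed or false result become a practical risk. All bias figures are illustrations that rest on assumed values and the plan's SD of 8 h. The sample size calculation itself is not in error.

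**What to change.** **Primary analysis.** In section 7.3 and the Study Summary, specify one linear model for pre-delivery hospital hours: group + parity stratum + BMI stratum + baseline Bishop score + gestational age at arrival. Report the adjusted mean difference with a 95% CI from a robust (HC3) standard error. Keep the unadjusted t-test and Wilcoxon test as sensitivity analyses. Fix the model before outcome data are examined, so that adjustment is not chosen from the baseline tests.

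**Data.** List baseline Bishop score for both groups in section 3.3, abstracted from the arrival exam. State a rule for missing control scores, for example multiple imputation from the model terms and outcome, with a complete-case check. Gestational age at arrival can be derived from gestational age and time of delivery, both listed for both groups, and the admission time.

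**Limitation.** State that confounding by unmeasured factors, such as preference for going home, remains.

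**Cost.** SAP wording, one or two abstracted fields and four model degrees of freedom. In the assumed case of two covariates imbalanced by 0.5 SD that explain nothing, power is about 77% (75% with HC3). The loss is recovered once the model terms explain about 7% of outcome variance. If control scores are often uncharted, abstraction will take more work than this and the missing-data rule will carry more weight.

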    1. Informed consent will be obtained by a trained research coordinator, Principal Investigator, Co-Principal Investigator, or authorized obstetric provider.
  - C. Randomization
    1. Randomization will occur the day before the planned induction to decrease drop out (for example: from spontaneous labor between the clinic visit and planned induction).
    2. The randomization will be computer generated.
    3. The patient's randomization status will be accessed by the research coordinator.
    4. The research coordinator will contact the patient by phone to inform her of her randomization group.

5. Randomization will be stratified by parity (primiparous vs. multiparous) and by body mass index (current body mass index  $<30 \text{ kg/m}^2$  vs.  $\geq 30 \text{ kg/m}^2$ ).

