### III. Enrollment of participants (Prospective Study)

#### A. Enrollment of outpatient intervention participants

1. Clinic nurses, clinical assistants who room patients and the patient's obstetric provider will refer eligible patients to the research coordinator.
2. The study coordinator will screen the induction scheduling book in the Family Birth Center weekly to identify patients who may be eligible for the study. She will communicate with eligible women by telephone share general information about the study. If women are interested in learning more, she will meet with them at the patient's next clinic appointment.
3. Patients who receive their care in Mayo Clinic Family Medicine clinics will be eligible for this study. Their providers will be educated regarding this study. These women will be enrolled in the same manner as women from the antenatal clinic.

- (a) Patient education and consent
  - (a) The patients will be educated about induction of labor, the Foley catheter, and the proposed research study.
  - (b) If the patient elects participation, she will undergo informed consent at that time by a trained research study coordinator, Principal Investigator, Co-Principal Investigator, or authorized obstetric provider.
  - (c) Parity (primiparous vs. multiparous) and BMI (current body mass index  $<30 \text{ kg/m}^2$  vs.  $\geq 30 \text{ kg/m}^2$ ) will be recorded based on the stratification used in the Randomized Control Trial design.

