## 7.2 Sample Size Determination for Prospective Study

A power analysis was performed and assumed a standard deviation of 8 hours. With 40 subjects in the Foley intervention arm and 160 subjects in the standard of care group, we would have 80% power to detect a  $\frac{1}{2}$  standard deviation reduction in the predelivery hospitalization time from 16 to 12 hours in the standard of care and intervention groups, respectively. This also assumes a 2-sided significance level of 0.05.

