### Secondary Hypotheses:

The secondary hypotheses are described below, followed by the statistical tests we plan to utilize.

1. Cesarean delivery rates will not differ between the two groups. This hypothesis will be tested using the Chi-Square or Fisher's exact test. Graphical and statistical methods will be used to show the data descriptively. We will report frequencies and percentages.

2. Maternal outcomes (including but not limited to postpartum hemorrhage, infection, hospital readmission rates, and satisfaction scores) will not differ between the two groups. These hypotheses will be assessed using the Chi-Square or Fisher's exact test for categorical endpoints. For continuous endpoints, a 2-sample t-test or the nonparametric equivalent (Wilcoxon Rank-Sum test) will be used. Graphical and statistical methods will be used to show the data descriptively. For continuous data, we will also report means, medians, standard deviations, and ranges. For categorical data, we will report frequencies and percentages.

3. Fetal outcomes (including but not limited to APGAR scores, umbilical artery pH, and nursery disposition) will not differ between the two groups. These hypotheses will be assessed using the Chi-Square or Fisher's exact test for categorical endpoints. For continuous endpoints, a 2-sample t-test or the nonparametric equivalent (Wilcoxon Rank-Sum test) will be used. Graphical and statistical methods will be used to show the data descriptively. For continuous data, we will also report means, medians, standard deviations, and ranges. For categorical data, we will report frequencies and percentages.

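### Controls are matched 4:1 on parity and BMI stratum, but the planned tests ignore the strata, so the standard error is somewhat too large and part of the precision from matching is forgone

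*Combined protocol and SAP*

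**What the plan says.** Section 3.1 (General Design) states that "a prospective design with an outpatient intervention group (Foley catheter) and matched inpatient control comparison group is proposed". The enrollment rules for the comparison group in the same section make this concrete: "Four inpatient comparison control participants will be enrolled with the same parity and BMI strata for every outpatient intervention patient enrolled". The factors are parity (two classes) and current BMI (below 30, or 30 and above), which gives four strata. They come from the randomized stage, where "Randomization will be stratified by parity (primiparous vs. multiparous) and by body mass index"; section 5.3 repeats this. For outpatient women in the prospective stage, the two factors "will be recorded based on the stratification used in the Randomized Control Trial design".

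The analysis does not use them. The primary hypothesis in section 7.3 reads: "The mean time spent in the hospital between the groups will be compared using a 2-sample t-test or the nonparametric equivalent (Wilcoxon Rank-Sum test". The Study Summary agrees: the mean times "will be compared using a two sample t-test or the nonparametric equivalent Wilcoxon rank sum test". For cesarean delivery, section 7.3 says "This hypothesis will be tested using the Chi-Square or Fisher's exact test", and the other maternal and fetal outcomes get the same kinds of unstratified test. Nothing in section 7 mentions a stratified, matched or covariate-adjusted analysis. Section 7.2 sizes the study for independent samples, starting "With 40 subjects in the Foley intervention arm and 160 subjects in the standard of care group", and gives no within-stratum SD or correlation.

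**The concern.** A design that fixes the stratum mix to be equal in both groups should have an analysis that knows it. If parity and BMI class predict time to delivery, part of the 8-hour SD is variation between strata. Matching stops that part from contributing to the sampling error of the group difference, but a two-sample t-test leaves it in the pooled SD. The point estimate benefits from the matching; the reported standard error, confidence interval and p-value do not show it.

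This is about the error bar and would arise even with no confounding. It is separate from the question of adjusting a non-randomized comparison for factors that were not matched. At stake is precision in a study with 40 outpatient women, whose design was changed because enrollment was difficult, and which goes to the trouble of finding four stratum-matched controls for each of them.

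**Working it through.** **Inputs from section 7.2:** 40 and 160 women, SD 8 h, means 16 and 12 h (difference 4 h), two-sided 0.05. **Assumption:** R², the share of the 8-hour variance explained by the four strata. The documents give no value, so a range is shown.

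**Step 1, the plan's own figure.** SE = 8 × sqrt(1/40 + 1/160) = 1.414 h; 4/1.414 = 2.83. Power from the noncentral t with 198 degrees of freedom is 80.4%. The stated 80% reproduces, for an independent-samples test with no credit for matching.

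**Step 2, the effect of matching.** With exactly four controls per outpatient woman in every stratum, the actual SE of the difference is 8 × sqrt(1−R²) × sqrt(1/40 + 1/160) = 1.414 × sqrt(1−R²). The planned t-test still reports about 1.414.
- Overstatement of the SE: 1/sqrt(1−R²).
- Type I error of the planned test: 2 × [1 − Φ(1.96/sqrt(1−R²))].
- Power of the planned test: about Φ[(4 − 1.96 × 1.414)/actual SE].
- Power with stratum adjustment: noncentral t with the actual SE and 200 − 5 = 195 degrees of freedom.

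| Assumed R² | Actual SE (h) | Reported SE too large by | Type I error, planned | Power, planned | Power, adjusted |
|---|---|---|---|---|---|
| 0 | 1.414 | 0% | 5.0% | 80% | 80% |
| 0.05 | 1.378 | 2.6% | 4.4% | 81% | 82% |
| 0.10 | 1.342 | 5.4% | 3.9% | 82% | 84% |
| 0.20 | 1.265 | 11.8% | 2.8% | 83% | 88% |

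**Step 3, simulation.** Four equal strata, each with 10 outpatient women and 40 controls, normal outcomes, 20,000 trials per setting. At R² = 0 both tests have 80.5% power. At R² = 0.10 the planned t-test rejects 4.0% of the time under no difference; power is 81.8%, against 84.7% adjusted. At R² = 0.20 it rejects 2.9%; power is 83.0% against 88.2%. The unstratified Wilcoxon test is similarly conservative.

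**Step 4, what the range implies.** If parity carried all of R² and split the women equally, the gap in mean hours between primiparous and multiparous women would be 2 × 8 × sqrt(R²): 3.6 h at 0.05, 5.1 h at 0.10 and 7.2 h at 0.20. The assumed standard-of-care mean is 16 h.

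**Step 5, imperfect balance.** With 20% of women lost at random (an assumption) and R² = 0.20, type I error of the planned test is about 3.2%, nearer to nominal than the 2.8% under exact balance. Power is then 72% against 80% with adjustment; both are lower partly because fewer women remain.

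**The case against.** The strongest reply is that no claim in the plan fails. The stated power is right for the named test, that test keeps at least 80% power at every R² with the planned numbers, and its type I error never exceeds 5%. That stands, and it limits the point to forgone precision.

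The size also rests wholly on an R² the documents do not give. At 0.10 or below, the loss is under three points of power. Choosing parity and BMI for both stratification and matching suggests that the investigators expect them to matter, but it does not say by how much.

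Exact 4:1 balance is an idealization. Section 4.3 expects about 50 of 250 consenting women to become ineligible, and section 7.3 excludes women with a missing primary outcome. Section 7.4 leaves out elective withdrawals and also analyzes randomized-stage women, who were stratified but not matched 4:1, without saying whether the stages are pooled. Imbalance reduces the overstatement of the SE without removing it. It is also a reason to adjust, since the named tests do not correct for any stratum imbalance that results.

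Four stronger readings are tempting and not supported:
- **The study is underpowered, or false positives are inflated.** Step 1 and the table show neither.
- **All the benefit of matching is lost.** The estimate keeps its balance, and the planned test's power rises with R².
- **The loss is very large, as it would be if strata explained half the variance.** By the formula in step 4 that needs a gap of 2 × 8 × sqrt(0.5) = 11.3 h between parity groups; nothing in the documents suggests it.
- **Conservative secondary tests favor the hypothesis of no difference.** With assumed cesarean rates of 30% and 5% by parity, the unstratified chi-square rejects about 3.8% of the time instead of 5%. That is roughly one percentage point, on rates the documents do not contain, and too little to support a claim of bias.

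**Conclusion.** The mismatch is real: controls are matched by stratum in section 3.1, and the Study Summary and section 7.3 name only unstratified tests. The consequence is a conservative primary test that gives up part of the precision that matching provides. At an assumed R² of 0.20 the standard error is about 12% too large, type I error is about 2.8%, and about five points of power are forgone (83% against 88%). At 0.10 the standard error is about 5% too large and the loss is two to three points; at zero there is none. These figures assume exact 4:1 balance, a total SD of 8 h and normal outcomes. The 80% in section 7.2 can stay as a conservative figure. This is a worthwhile and nearly free improvement in efficiency. It does not threaten the validity of the primary conclusion.

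**What to change.** In section 7.3 and the Study Summary:
- **Primary outcome:** make the analysis a linear model of pre-delivery hospital hours on group plus the four parity-by-BMI strata, and report the adjusted difference with its 95% confidence interval.
- **Rank test, if kept:** use the stratified (van Elteren) form of the Wilcoxon test.
- **Cesarean and other categorical outcomes:** use the Cochran-Mantel-Haenszel test over the same strata, or over parity alone where events are sparse.

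Define the strata by the classes used at enrollment. Those rest on current BMI, whereas the baseline list in section 3.3 names pre-pregnancy BMI.

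The cost is a few sentences and three degrees of freedom. No new data are needed, because a control cannot be matched without knowing her stratum. If the strata explain nothing, power is essentially unchanged (80% either way).
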